
	
Day 1: Following \geq 10 hour overnight fast, in the morning on Day 1, fasting blood samples will be taken for the assessment of various metabolic parameters as well as for banking for future exploratory measurements.
 
Thereafter, an OGTT will be performed over 180 min as a baseline assessment. Standardized meals will be provided following the OGTT and in preparation of the clamp, that will be performed on the next day.
 
Approximately around/after 22:00 h, subjects will receive a low-dose overnight intravenous (IV) infusion of insulin to titrate the BG to a target level of 100 mg/dl (\pm 10%) in preparation for the H-E clamp.
 
Approximately at midnight, a primed-continuous IV infusion of stable isotope labeled glucose ($[6,6-^2\text{H}_2]\text{glucose}$) will also be initiated for the measurement of EGP.
 
Day 2: After completing the fasting EGP assessments, subjects will undergo a 6-hour H-E clamp with stable isotope labeled glucose.
 
Following their glucose clamp, subjects will be monitored post clamp to ensure adequate glycemic stabilization. They will be provided with a standardized meal and may then be released home.
 
Telephone Visits: Subjects will be contacted every other day until they come in for the next in-house period, to remind the subjects of their diet and exercise regimes and to check subjects BG.
 
Outpatient Visit(s):
 
Subjects will check-in on Day 8 for their outpatient visit. A sensor change of the CGMS device will be performed. Blood samples will be taken for safety assessments. A urine pregnancy test (if applicable), and urine drug screen and alcohol breath test will be collected. Subjects will be re-instructed to maintain their usual diet and physical activity regimes.
 
In-house Period 2:
 
Day 15: Subjects will check in to the clinic in fasting conditions on Day 15 for a 4-day in-house period. A urine pregnancy test (if applicable), and urine drug screen and alcohol breath test will be collected. Blood samples will be taken in the fasting state prior to any assessment for the analysis of FPG, safety parameters, various metabolic parameters, as well as for banking for future exploratory measurements.
 
They will get re-instructed to maintain their regular diet and physical activity. Subjects will receive standardized meals throughout their in-house stay. Food intake will be recorded during the entire in-house period by study staff.
 
Subjects will undergo the first of three ultrasound insonifications (following \geq 10 hour overnight fast). Insonifications will be performed on three consecutive days (Days 15, 16 and 17). Subjects will be insonified by the stimulus pulse for 15 minutes on each day for a total of 45 minutes per study. Breath holds and image targeting will extend the total duration that the probe is on the subject (without the stimulus). Insonification will be performed, starting at approximately between 07:00 h and 08:30 h.

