Subjects will check in to the clinic in fasting conditions on Day 15 for a 4-day in-house period. Check-in assessments will be performed to ensure subjects meet the check-in requirements. A urine pregnancy test (if applicable), and urine drug screen and alcohol breath test will be collected. Fasting blood samples will be taken prior to any assessment for the analysis of safety parameters, various metabolic parameters, as well as for banking for future exploratory measurements.

Subjects will undergo the first of three ultrasound insonifications (following ≥ 10 hour overnight fast). If sonographer is not able to visualize or stimulate target area during the first ultrasound insonification, or a measured distance from the skin surface to the porta hepatis target exceeds 10 cm, the subject will be excluded from the study. Excluded subjects may be replaced. Insonifications will be performed on three consecutive days (Days 15, 16 and 17). Subjects will be insonified by the stimulus pulse for 15 minutes on each day for a total of 45 minutes/study. Breath holds and image targeting will extend the

total duration that the probe is on the subject (without the stimulus). Insonifications will be performed between 07:00 h to 08:30 h.

Subjects will receive standardized meals after the insonification and throughout their in-house stay. Food intake and exercise will be recorded during the entire in-house period by study staff.

Subjects will be re-instructed on maintaining their regular diet and physical activity regimens.

Day 16:

Following \geq 10 hour overnight fast, in the morning of Day 16, subjects will undergo the second of three ultrasound insonifications. Insonification for each subject will take place at approximately the same time of day as on Day 15.

Thereafter, at approximately 08:00 h-09:00 h, an OGTT will be performed over 180 min. OGTT should start at approximately the same as on Day 1 for the subject. Standardized meals will be provided following the OGTT and in preparation of the clamp, that will be performed on the next day.

Approximately around/after 22:00 h, subjects will receive a low-dose IV infusion of insulin to titrate the BG to a target level of 100 mg/dl (\pm 10%) in preparation for the H-E clamp. Approximately at midnight, a primed-continuous IV infusion of stable isotope labeled glucose will also be initiated for the measurement of EGP.

Day 17:

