6.3 Rationale for Study Design and Endpoints

The aim of this exploratory, pilot study is to determine the effect of hepatic ultrasound insonification on insulin sensitivity, glycemic, metabolic and lipid parameters, as well as on various biomarkers in subjects with T2DM.

Subjects with T2DM will participate in the study, as these subjects are an important target population. These subjects are characterized by relative rather than absolute insulin deficiency in association with variable degrees of insulin resistance.

Subjects on metformin therapy will continue the stable drug dose throughout the entire study.

Subjects will be supplied with a CGMS to ensure that blood glucose levels are monitored closely. CGM as assessment has been chosen to assess the ultrasound insonification effects with a standardized method for efficacy. As assessment of insulin secretion and resistance, an OGTT and H-E clamp will be performed.

Whole-body insulin sensitivity will be assessed with the 2-step H-E clamp procedure. The use of two-stepped IV insulin infusions is used in combination with IV stable isotope labeled glucose infusion to allow the differentiation between hepatic (EGP) and peripheral insulin sensitivity.

Due to the variability in fasting blood glucose concentrations in subjects with diabetes mellitus, which might affect the metabolic response, an overnight baseline period will be

used to establish the target plasma glucose concentration of 100 mg/dL ($\pm 10\%$) prior to fasting EGP measurements.

Endogenous glucose production will be measured in the fasting state prior to the start of the clamp and suppression of EGP during step 1 of the 2-step H-E clamp. It will be assessed using a stable isotope labeled glucose ($[6,6-^2\text{H}_2]\text{glucose}$) tracer method.

Insulin will be infused at a low dose, followed by a high dose. During the low-dose IV insulin infusion, EGP will be partially suppressed, while during the high dose IV insulin infusion, EGP will be near completely suppressed.

Metabolic changes in response to glucose ingestion will be assessed via an OGTT. It will be performed to assess the postprandial carbohydrate metabolism to see changes in insulin and glucose response.

The other glucometabolic endpoints of this study are chosen to investigate additional ultrasound insonification effects.

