16.0 APPENDIX**Table 16-1 Schedule of Events (SOE)**

ASSESSMENTS	SCREEN	IN-HOUSE PERIOD 1			OPV	IN-HOUSE PERIOD 2			OPV	F/U
		Observational Period 1 (Days -1 to Day 14)				Insonification (Days 15-17)				
Visit/ Timepoint (Day)	Start Day -28	-1	1	2	8	15	16	17	18	22
Study Intervention/ Insonification						X	X	X		
Informed consent	X									
Assess eligibility criteria	X									
Demography	X									
Medical history	X									
Sequestered in clinic/unit		X	X	X		X	X	X		
Physical examination (PE)	X									
Abbreviated PE		X				X			X	X
Hematology, serum chemistry & urinalysis	X	X				X			X	X
Coagulation	X									
TSH	X									
HbA1c	X	X				X			X	X
Hep B, Hep C, HIV	X									
Pregnancy test (urine)		X			X	X			X	X
Pregnancy test (serum)	X									
FSH if postmenopausal	X									
Urine drug screen & alcohol breath test	X	X			X	X			X	X
Weight, BMI	X	X	X		X	X		X	X	X
Height	X									
Vital signs	X	X	X	X	X	X	X	X	X	X
12-lead ECG	X	X		X		X		X		X
Instructions on SMBG /glucose via fingerstick to measure during outpatient periods (Days 3- 14 and 19-27)		X								

ASSESSMENTS	SCREEN	IN-HOUSE PERIOD 1			OPV	IN-HOUSE PERIOD 2			OPV	F/U	
		Observational Period 1 (Days -1 to Day 14)				Insonification (Days 15-17)					
Visit/ Timepoint (Day)	Start Day -28	-1	1	2	8	15	16	17	18	22	28
Study Intervention/ Insonification						X	X	X			
Record concomitant medications	X	X	X	X	X	X	X	X	X	X	X
Record ADEs	X	X	X	X	X	X	X	X	X	X	X
Standardized meals		X	X	X		X	X	X	X		
CGMS		X	X	X	X	X	X	X	X	X	X
CGMS sensor insertion/ change		X			X				X		
Overnight fast \geq 10 hours			X	X	X	X	X	X	X	X	X
Check of imaging criteria						X					
OGTT			X				X				
Insulin and glucose tracer infusion overnight			X	X			X	X			
Blood sampling for EGP				X				X			
Initiation of Clamp procedure				X				X			
Fasting plasma glucose			X	X	X	X	X	X	X	X	X
HOMA-IR			X			X			X		X
Exploratory biomarkers for assessment and potential storage			X			X			X		X
Glucose parameters (e.g., Fructosamine)			X			X			X		X
Lipid metabolism parameters (e.g. FFA, triglycerides)			X			X			X		X
Inflammatory biomarkers (e.g., adiponectin, CRP)			X			X			X		X

Table 16-2 Schedule of Events (SOE) for Subjects with $BMI > 35.0 \text{ kg/m}^2$ and $\leq 40.0 \text{ kg/m}^2$ and/or Waist Circumference > 40 and ≤ 45 inches

ASSESSMENTS	SCREENING PERIOD	IN-HOUSE PERIOD 1		OPV	IN-HOUSE PERIOD 2			OPV	F/U		
		Observational Period 1 (Days -1 to Day 14)			Insonification (Days 15-17)						
Visit/ Timepoint (Day)	Start Day—50	-1	1	2	8	15	16	17	18	22	28

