Study Intervention/ Insonification						X	X	X			
Informed consent	X										
Assess eligibility criteria	X										
Re-assess eligibility criteria		X**									
Demography	X										
Medical history	X										
Sequestered in clinic/unit		X	X	X		X	X	X	X		
Physical examination (PE)	X										
Abbreviated PE		X				X			X		X
Hematology, serum chemistry & urinalysis	X	X				X			X		X
Coagulation	X										
TSH	X										
HbA1c	X	X				X			X		X
Hep B, Hep C, HIV	X										
Pregnancy test (urine)		X			X	X				X	X
Pregnancy test (serum)	X										
FSH if postmenopausal	X										
Urine drug screen & alcohol breath test	X	X			X	X				X	X
Weight, BMI	X	X	X		X	X		X		X	X
Height	X										
Waist circumference	X										
Hepatic ultrasound (Screening only)	X										
Vital signs	X	X	X	X	X	X	X	X	X	X	X
12-lead ECG	X	X		X		X		X			X

ASSESSMENTS	SCREENING PERIOD	IN-HOUSE PERIOD 1		OPV	IN-HOUSE PERIOD 2			OPV	F/U		
		Observational Period 1 (Days -1 to Day 14)			Insonification (Days 15-17)						
Visit/ Timepoint (Day)	Start Day—50	-1	1	2	8	15	16	17	18	22	28
Study Intervention/ Insonification						X	X	X			
Instructions on SMBG /glucose via fingerstick to measure during outpatient periods (Days 3-14 and 19-27)		X									
Record concomitant medications	X	X	X	X	X	X	X	X	X	X	X
Record ADEs	X	X	X	X	X	X	X	X	X	X	X
Standardized meals		X	X	X		X	X	X	X		
CGMS		X	X	X	X	X	X	X	X	X	X
CGMS sensor insertion/ change		X			X				X		
Overnight fast ≥ 10 hours			X	X	X	X	X	X	X	X	X
Check of imaging criteria						X					
OGTT			X				X				
Insulin and glucose tracer infusion overnight			X	X			X	X			
Blood sampling for EGP				X				X			
Initiation of Clamp procedure				X				X			
Fasting plasma glucose			X	X	X	X	X	X	X	X	X
HOMA-IR			X			X			X		X
Exploratory biomarkers for assessment and potential storage			X			X			X		X
Glucose parameters (e.g., Fructosamine)			X			X			X		X
Lipid metabolism parameters (e.g. FFA, triglycerides)			X			X			X		X
Inflammatory biomarkers (e.g., adiponectin, CRP)			X			X			X		X

*Study Visit to be performed \geq 30 days after hepatic ultrasound screening examination.

**Necessary laboratory analyses and examinations need to be performed prior to Day -1, so that all eligibility criteria from screening can be re-assessed on Day -1. Re-assessment can be performed after a 30-day wait period, starting after the ultrasound examination.

Table 16-3 Toronto Clinical Neuropathy Scoring System

Toronto Clinical Neuropathy Scoring System		

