The primary insonification analysis period for CGMS parameters will be from 14:00h on Day 15 to 22:00h on Day 16, omitting data collected between a subjects OGTT glucose consumption start time + 180 minutes.

The CGMS parameters will be summarized in a table using descriptive statistics for the primary insonification analysis period and change from baseline. The CGMS parameters for the baseline period, primary insonification analysis period and Days 19 and 20 will be listed.

The percent of time spent in defined glucose ranges will be calculated separately for each of the analysis periods along with the change from the baseline period. The following glucose ranges will be defined and presented separately:

- > 250 mg/dL (>13.9 mmol/L)
- > 180 mg/dL (>10.0 mmol/L)
- 70-180 mg/dL (3.9-10.0 mmol/L)
- < 70 mg/dL (<3.9 mmol/L)
- < 54 mg/dL (<3.0 mmol/L)

Average daily glucose will be calculated based on the applicable glucose measurements obtained during the specified day/period.

To calculate the LBGI and HBGI, the original BG data for each day/period is transformed such that it is centered by zero and bound between $-\sqrt{10}$ and $\sqrt{10}$.

$$f(BG, \alpha, \beta) = [(\ln(BG))^{1.084} - 5.381] * 1.509$$

The transformed values are then inputted into the BG risk function:

$$r(BG) = 10 * f(BG, \alpha, \beta)^2$$

The risk of each observation is further transformed into two series, risk of low BG series, $rl(BG)$, and risk of high BG series, $rh(BG)$:

$$rl(BG) = r(BG) \text{ if } f(BG) < 0 \text{ and } 0 \text{ otherwise}$$

$$rh(BG) = r(BG) \text{ if } f(BG) > 0 \text{ and } 0 \text{ otherwise}$$

These series are then averaged to produce the LBGI and the HBGI as follows:

$$LBGI = \frac{1}{n} \sum_{i=1}^n rl(x_i)$$

$$HBGI = \frac{1}{n} \sum_{i=1}^n rh(x_i)$$

Absolute values and changes from baseline will be summarized using descriptive statistics for BG, HOMA2-IR, HOMA2-B, and FPG. Baseline is defined as the last non-missing value collected prior to a subject's first HUI. The HOMA2 results will be produced by the HOMA2 calculator with fasting plasma glucose and insulin concentration obtained from safety laboratory

assessments as the inputs. Summaries will be provided by study visit/time point as applicable in the protocol Schedule of Events.

For BG, coefficient of variation (CV) calculated as $100 \times [\text{standard deviation (SD)} \div \text{mean}]$ will be included with the other summary statistics.

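### Day 17 FPG is drawn under overnight IV insulin but compared with an insulin-free Day 15 baseline, so that visit's change mainly reflects the infusion target

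*SAP*

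**What the plan says.** Change from baseline in FPG is a secondary endpoint (Protocol 5.2, SAP 2.2). SAP 6.9, under Glucose metabolism parameters, sets out the analysis in three sentences:

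- what is summarized: "Absolute values and changes from baseline will be summarized using descriptive statistics for BG, HOMA2-IR, HOMA2-B, and FPG";
- the baseline: "Baseline is defined as the last non-missing value collected prior to a subject's first HUI";
- the visits: "Summaries will be provided by study visit/time point as applicable in the protocol Schedule of Events".

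The row "Fasting plasma glucose" in the Schedule of Events (Protocol Tables 16-1 and 16-2) marks Days 1, 2, 8, 15, 16, 17, 18, 22 and 28. The row "Insulin and glucose tracer infusion overnight" marks Days 1, 2, 16 and 17.

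For Day 15 the Protocol summary (section 2.0) says: "Blood samples will be taken in the fasting state prior to any assessment for the analysis of FPG, safety parameters". For the evening of Day 16, Protocol 6.2 says that "subjects will receive a low-dose IV infusion of insulin to titrate the BG to a target level of 100 mg/dl", within 10%. Protocol 9.1.20 aims for 100 ± 10 mg/dL over the last two hours before the fasting EGP period and allows IV glucose if a subject is below target. Protocol 6.3 gives the reason for this overnight period: "Due to the variability in fasting blood glucose concentrations in subjects with diabetes mellitus", which could affect the metabolic response.

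The only caveat about FPG is in Protocol 9.1.13 and concerns evenings when hypoglycemia was treated. It does not mention the overnight insulin.

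**The concern.** The baseline and the Day 17 value are measured under different conditions. Day 15 FPG is the subject's own fasting glucose. Day 17 FPG is glucose held near a set level by titrated insulin. Their difference mostly shows how far the subject started from 100 mg/dL. A fall can appear when the device does nothing, and a real effect would be largely absorbed by the titration.

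The study has no control arm in which the same fall would show up. The affected visit is the day of the third insonification, where a reader would look for an effect. Protocol 4.2 describes a biological effect in terms of statistically significant change in the primary and secondary markers, and SAP 5 leaves room for testing at the 5% level. A large Day 17 fall could therefore be read as evidence for the device.

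**Working it through.** The documents state no figure on this point, so there is none to reproduce. The check has four steps.

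**1. Which visits are affected.** Of the nine FPG days, those after the first insonification are Days 16, 17, 18, 22 and 28. The overnight infusion covers the mornings of Days 2 and 17. So 1 of 5 post-insonification FPG visits falls under infusion. Day 2 precedes the baseline; it would become the baseline only if both Day 15 and Day 8 were missing. If Day 15 alone is missing, Day 8 serves, also without infusion. HOMA is scheduled on Days 1, 15, 18 and 28 and is not affected.

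**2. Is a fasting Day 17 draw always inside the infusion or clamp?** The draw time is not given. Table 9-3 shows overnight insulin from 22:00 to 9:00, Step 1 from 9:00 to 12:00 and Step 2 from 12:00 to 15:00, with no gap. The earliest insonification start, 07:00, is already about 9 hours into the infusion. As scheduled, any fasting draw that morning falls within this span.

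**3. Size of the artefact with no device effect.** Let FPG15 be the Day 15 value and *a* the share of the gap to target closed by the time of the draw:

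change = *a* × (100 − FPG15)

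The FPG15 and *a* values below are assumed for illustration; they are not bounds.

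| Assumed FPG15 (mg/dL) | *a* = 1 (range for target 90 to 110) | *a* = 0.8 | *a* = 0.5 |
|---|---|---|---|
| 150 | -50 (-60 to -40) | -40 | -25 |
| 110 | -10 (-20 to 0) | -8 | -5 |
| 70 | +30 (+20 to +40) | +24 | +15 |

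The last row depends on the optional IV glucose.

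With a true device effect *d* on free fasting glucose, the change becomes *a* × (100 − FPG15) + (1 − *a*) × *d*. At *a* = 1 the effect drops out. At *a* = 0.5, FPG15 = 150 and *d* = -20, the change is -25 − 10 = -35, of which only -10 is due to the device.

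A simulation with assumed baseline mean/SD of 130/20, 150/30 and 170/35 mg/dL (day-to-day SD 12) and Day 17 held between 90 and 110 gave mean changes of about -30, -50 and -70. These were the same for true effects of 0, -10 and -20, and the correlation of change with baseline was -0.97 to -0.99. The insensitivity to the true effect follows from assuming that the target is met; it is not separate evidence.

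**4. Would Day 2 rescue the comparison?** Conditions match, but both values are held at the same target: (90 to 110) − (90 to 110) gives -20 to +20, centred on 0 by design. That removes the artefact and also removes almost any device signal.

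For contrast, the SAP 6.9 CGMS windows end at 22:00 on Day 1 and Day 16, when the infusions start. The SAP gives no reason for these limits, but they keep infusion-controlled glucose out of the CGMS summaries. FPG has no such limit.

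**The case against.** The strongest reply is that little is at stake and the sizes are uncertain. FPG is summarized descriptively, with no test planned in SAP 6.9. Absolute values are tabulated, so Day 2 can be read beside Day 17, and all data are listed by subject. The Schedule of Events itself shows the infusion on Days 16 and 17. All of this stands and is why the point is minor.

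The Day 17 draw time is also unstated. The Day 17 narrative does not mention an FPG sample, so only the Schedule row creates it, and the Operations Manual is not available here. An early draw might precede full control at target. This stands as a limit on size: partial closure shrinks the artefact, and a baseline near 100 makes it small. In neither case does the Day 17 change become a measure of untreated fasting glucose.

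The assumed 70 mg/dL baseline sits at the lower FPG contact limit and is an unlikely case in subjects with HbA1c above 6.5%. That is fair; it only shows that the direction can reverse.

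Day 18 is the morning after a clamp, so it may differ from Day 15 in other ways. The documents do not settle this. The claim is only that Days 16, 18, 22 and 28 are not drawn under the overnight infusion.

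Finally, a footnote could prevent misreading without dropping a visit. It would help, but the table would still carry a change figure with no useful interpretation.

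**Conclusion.** The concern holds. Followed as written, the SAP produces a Day 17 FPG change set mainly by insulin titration. This rests on the SAP's reference to the Schedule of Events, the Day 17 mark in the FPG row, and the continuous insulin in Table 9-3; it does not depend on any assumed glucose value. The size does depend on one: about 100 minus the Day 15 value if the target is met, and less if titration is incomplete.

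Severity is minor. The general baseline rule in SAP 5.4 is not at fault, the other four post-insonification visits do not carry this artefact, and the primary M/I endpoint compares Day 17 with Day 2 (SAP 6.7).

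**What to change.** Amend SAP 6.9 only. Leave Day 17 out of the FPG change-from-baseline summary, and list Day 2 and Day 17 FPG with a flag that they were taken under IV insulin infusion. If a Day 17 change is shown at all, show it only against Day 2, with a note that both values are held at the same target and say almost nothing about a device effect. SAP 5.4 stays as it is.

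The cost is one sentence in SAP 6.9, one visit removed from one table and one listing flag. No new data are needed. If the analysis has already begun, SAP 7 provides for describing the change in the CSR.

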6.2 Study Description

Screening Visit:

At Screening, potential subjects for the study will be provided with written and oral information about the study and the procedures involved. Subjects have to sign the institutional review board (IRB) informed consent form (ICF) prior to entering the study.

The Screening Visit will be performed up to 28 days prior to the first in-house period, to identify eligible subjects for the study. For eligible subjects with a BMI > 35.0 and ≤ 40.0 kg/m² and/or waist circumference > 40 and ≤ 45 inches, an ultrasound examination will be added to the screening assessments to confirm eligibility. For these subjects, the screening period will be extended for at least 30 days, starting after the ultrasound examination has been performed. Eligibility per inclusion and exclusion criteria will be re-assessed in a second screening visit prior to the first In-house Period.

All assessments performed at the Screening visit are stated in the [Schedule of Events \(SOE\)](#) and will be recorded in the electronic case report form (eCRF). See section [9.1.2](#) and [11.2](#) for further details.

In-house Period 1:

Day -1:

Subjects will check in to the clinic in the morning on Day -1 for a 3-day in-house period. Check-in assessments will be performed to ensure subjects meet the check-in requirements. A urine pregnancy test (if applicable), and urine drug screen and alcohol breath test will be collected. Blood samples will be taken for safety assessments.

Subjects get instructions on maintaining their current diet and physical activity.

Subjects will receive standardized meals throughout their in-house stay. Food intake will be recorded during the entire in-house period by study staff.

Subjects will be connected to a CGMs (e.g., Dexcom G6) and will continue wearing this for the entire study period. Subjects will be blinded to the CGMS data. Monitoring data from Day -1 to Day 14 will be used for the baseline monitoring evaluation. Subjects will be provided with a glucometer. They will be instructed on how to use the glucometer and to monitor their fasting plasma glucose levels daily during the outpatient periods. They will be instructed to contact the study staff, if FPG > 220 mg/dL, they experience symptoms of hypoglycemia, or measures an FPG < 70 mg/dL. Subjects will be frequently contacted by qualified study site staff to review their fasting plasma glucose values.

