It will be ensured that subjects have an adequate fasting time prior to the assessments on Day 1.

Day 1:

Following ≥ 10 hour overnight fast, in the morning on Day 1, blood samples will be taken in the fasting state for the assessment of various metabolic parameters and biomarkers, as well as for banking for future exploratory measurements.

Thereafter, at approximately 08:00 h-09:00 h, an OGTT will be performed over 180 min as a baseline assessment. Standardized meals will be provided following the OGTT and in preparation of the clamp, that will be performed on the next day.

At approximately 22:00 h, subjects will receive a low-dose intravenous (IV) infusion of insulin (e.g., NovoLog®) to titrate the BG to a target level of 100 mg/dl ($\pm 10\%$) in preparation for the H-E clamp. Approximately at midnight, a primed-continuous IV infusion of stable isotope labeled glucose ($[6,6-^2\text{H}_2]\text{glucose}$) will also be initiated for the measurement of EGP.

Day 2:

After completing the fasting EGP assessments, subjects will undergo a 6-hour H-E clamp with stable isotope labeled glucose as baseline assessment. Blood sampling during the clamp will follow time points as indicated in the Clamp Sampling Schedule. Following their glucose clamp, subjects will be monitored post clamp to ensure adequate glycemic stabilization. They will be provided with a standardized meal and may then be released home.

Telephone Visits:

Subjects will be contacted every other day until they come in for the next in-house period, to remind the subjects of their diet /exercise and to check subjects BG.

Outpatient Visit:

Subjects will check-in on Day 8 for their outpatient visit. A sensor change of the CGMS device will be performed. Blood samples will be taken in the fasting state prior to any assessment for the analysis of FPG A urine pregnancy test (if applicable), and urine drug screen and alcohol breath test will be collected. Safety parameters (vital signs, 12-lead ECG, and recording of concomitant medications and adverse device events) and metabolic parameters (body weight/BMI) will be assessed. Subjects will be re-instructed on maintaining their regular diet and physical activity regimes.

In-house Period 2:

Day 15:

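### The Day 16 FPG change is referenced to a home morning (Day 15), so it mixes setting with treatment; the closest pre-treatment match, Day 1, gets no paired change

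*SAP*

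**What the plan says.** SAP 6.9, under glucose metabolism parameters, plans descriptive summaries of absolute values and changes from baseline for FPG. The reference is fixed: "Baseline is defined as the last non-missing value collected prior to a" subject's first HUI. On visits it says: "Summaries will be provided by study visit/time point as applicable in the protocol Schedule of Events". The "Fasting plasma glucose" row of that schedule (protocol Tables 16-1 and 16-2) marks Days 1, 2, 8, 15, 16, 17, 18, 22 and 28.

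Protocol 2.0 says of Day 15: "Blood samples will be taken in the fasting state prior to any assessment for the analysis of FPG, safety parameters". Protocol 6.2 says of the same morning: "Subjects will check in to the clinic in fasting conditions on Day 15 for a 4-day in-house period". It then says: "Subjects will receive standardized meals after the insonification and throughout their in-house stay". Before that, subjects are at home on their regular diet: "Subjects will be contacted every other day until they come in for the next in-house period".

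The first stay starts with a morning check-in on Day -1, and there too "Subjects will receive standardized meals throughout their in-house stay". The Day 1 fasting bloods and the baseline OGTT follow the next morning.

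**The concern.** Two things start on Day 15: the in-house stay with standardized meals, and insonification. The FPG baseline is drawn before both, and the Day 16 value after both. The planned Day 16 change therefore carries whatever the move from home to clinic does to fasting glucose, together with whatever insonification does. There is no untreated arm to remove the first part.

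This matters because change in FPG is a listed secondary endpoint, and protocol 4.2 says a biological effect is to be judged by changes in the primary and secondary markers. Day 16 is also the only FPG in the treatment stay after the first insonification that follows neither an overnight insulin infusion (Day 17) nor a clamp on the previous day (Day 18). A reader looking for an early FPG response would look at that row.

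**Working it through.** The documents state no FPG effect, SD or setting effect, so there is no figure to reproduce. The check sets the schedule against the baseline rule.

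**Step 1: which value is the baseline.** Day 15 blood is drawn fasting before any assessment, so it is the last FPG before the first insonification. If it is missing, the rule falls back to Day 8, which is also a morning after a night at home.

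**Step 2: what precedes each FPG** (protocol 6.2, 9.1.20, 9.1.22 and Table 16-1).

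- Day 1: one in-house day with standardized meals, then an overnight fast; OGTT follows.
- Day 16: one in-house day with standardized meals, then an overnight fast; OGTT follows; at least one insonification already given.
- Days 8, 15, 22, 28: night at home, usual diet, overnight fast.
- Days 2 and 17: in-house, overnight insulin titrated to about 100 ± 10 mg/dL.
- Day 18: in-house, morning after the clamp.

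Day 1 is thus the nearest pre-treatment counterpart of Day 16, and Day 15 is a fair counterpart of Days 22 and 28.

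**Step 3: what each contrast contains.** Let *d* be the insonification effect present in the Day 16 sample, *s* the shift from a home morning to the first in-house morning in the second stay, *s′* the same shift in the first stay, and *t* any drift between Day 1 and Day 16. Treat drift over the single day from Day 15 to Day 16 as negligible. Then on average:

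- Day 16 − Day 15 = *d* + *s*
- Day 16 − Day 1 = *d* + (*s* − *s′*) + *t*

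The first contrast cannot separate *d* from *s*. The second removes the setting shift if it is equal in both stays, but admits *t* over 16 − 1 = 15 days, or up to 15 + 5 = 20 days if Day 15 is moved within the window in protocol 9.1.12. Neither contrast is clean, and they fail in different ways.

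**Step 4: what showing both would reveal.** In subjects with all three values,

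(Day 16 − Day 15) − (Day 16 − Day 1) = Day 1 − Day 15.

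The gap between the two contrasts is therefore a purely pre-treatment quantity. It shows how far the choice of reference moves the result, without involving insonification at all.

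**Step 5: what the planned tables already give.** Day 1 and Day 16 absolute values are both summarized. In subjects with both values, the difference of the two means equals the mean paired change. The SD of the paired change does not follow from those summaries, because Var(Day 16 − Day 1) = Var(Day 16) + Var(Day 1) − 2 Cov(Day 16, Day 1), and the covariance is not tabulated. The median and quartiles of the paired change are not recoverable from the table either.

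**Step 6: how the SAP treats neighbouring endpoints.** The glucose-monitoring baseline runs from 14:00 on Day -1 to 22:00 on Day 1, and the treatment window from 14:00 on Day 15 to 22:00 on Day 16. The OGTT is scheduled only on Days 1 and 16. Clamp M, MCR and M/I pair Day 2 with Day 17 (SAP 6.7). FPG on the Day 16 morning is referenced to a home morning instead, and the SAP gives no reason. HOMA is not scheduled on Day 16, so it is unaffected.

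**The case against.** The strongest reply is that nothing is lost. SAP 6.9 summarizes absolute FPG at every scheduled visit and SAP 5 lists all data by subject, so the Day 1 to Day 16 change can be rebuilt. This stands. A reader might infer that the plan discards Day 1, and it does not. What is missing is the planned paired summary and a statement of how the Day 16 change is to be read.

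Second, no setting effect is documented. The in-house meals are designed to maintain weight (protocol 9.1.15), and subjects at home are told to keep their normal diet. At home they also check fasting glucose daily, are telephoned, and wear a blinded glucose sensor; check-in covers alcohol, drugs, medication and exercise. This also stands. A reader might infer that the clinic stay lowers FPG and that the Day 16 change is biased in a known direction. The documents do not support that; they support only that the two sources cannot be separated.

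Third, Day 1 is not an identical morning. The overnight-fast row begins at Day 1, so subjects may have eaten before check-in on Day -1, whereas on Day 15 they arrive fasting. Day 1 is also earlier, so drift and regression after HbA1c-based entry affect it more. This stands, and is why Day 1 should be added rather than substituted.

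Fourth, the last pre-treatment value is the conventional reference, the FPG analysis is descriptive, and no FPG test is specified. That limits the weight of the point but does not make Day 16 minus Day 15 interpretable by itself.

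Finally, protocol 9.1.24 puts insonification ahead of any other assessment, and the Day 16 text does not place the FPG draw before it. The Day 16 sample may therefore reflect one insonification or two.

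**Conclusion.** The point holds as a limited, inexpensive improvement. In this one-arm design, Day 16 minus Day 15 confounds the start of the in-house stay with the start of insonification in every subject, and the closest pre-treatment match has no planned paired change although the same SAP section uses that pairing for glucose monitoring. No numerical size can be given: the magnitude and sign of a setting effect are absent from the documents, and zero is possible. The Day 1 contrast helps to the extent that the setting shift is similar in both stays and drift over about two weeks is small.

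A reader might go further and conclude that Day 15 is the wrong FPG baseline throughout. That does not follow: Days 22 and 28 also come after a night at home, and Day 15 suits them.

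**What to change.** In SAP 6.9, for FPG:

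- Add the paired Day 16 minus Day 1 change, with n, mean, SD and the other planned descriptive statistics, beside Day 16 minus Day 15.
- Keep Day 15 as the reference for Days 22 and 28.
- State that Day 16 minus Day 15 alone is not read as an insonification effect, and that Day 16 minus Day 1 spans about two weeks (more if Day 15 is rescheduled) and is not a perfect match, so the two contrasts are read together.

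The cost is a few lines of SAP text and one extra row in the FPG table. No new samples or visits are needed, because FPG is already scheduled on Days 1, 15 and 16.
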